1. DOMAIN SUMMARY

1.1. Domain Summary

Strata	Myeloma, Non-Hodgkin Lymphoma and Chronic Lymphocytic Leukaemia
Domain-specific inclusion criteria	
 1. Patients must be receiving Ig (IV or subcutaneous - SC Ig) replacement for prevention of bacterial infections due to hypogammaglobulinaemia for at least 6 consecutive months. 2. Patient is eligible for trial of Ig cessation in the opinion of the treating clinician and local investigator. 3. Patient is willing and able to comply with each of the treatment arms.
Domain-specific exclusion criteria	
Patients will not be eligible for this domain if they fulfil any of the following criteria:
 
 1. Prior or planned allogeneic haematopoietic stem cell transplantation. 2. Major infection (Grade 3 or higher) in preceding 3 months, and/or current active infection requiring systemic antimicrobial treatment. 3. Already receiving systemic antibiotic prophylaxis for the purpose of preventing bacterial infection (NB: patients may receive antiviral, antifungal and PJP prophylaxis). 4. Intolerance of all trial antibiotic options in either arm A or arm B. 5. Communication, compliance or logistical issues that are likely to limit patient's ability to take prophylactic or emergency antibiotics, or to obtain urgent medical attention for symptoms of infection. 6. Pregnant or breastfeeding. 7. Severe renal impairment (estimated or measured creatinine clearance of < 30 mL/min). 8. Previous splenectomy. 9. Previous participation in this domain. 10. Treating team deems enrolment in the domain is not in the best interests of the patient.
Interventions to be compared	
Arm A: Stop Ig and commence prophylactic oral antibiotics. Once daily trimethoprim-sulfamethoxazole (co-trimoxazole) 160mg/800mg. NB: Doxycycline 100mg daily as an alternative for patients with hypersensitivity to co-trimoxazole.
 
Arm B: Stop Ig. Patients will be provided with amoxycillin/clavulanic acid 1750-2000mg/250mg and ciprofloxacin 750 mg to keep at home for initial use if symptoms of infection develop, with immediate review by their treating clinical team, or nearest emergency department or medical practitioner with phone contact to treating team if most practical.

	
NB: Clindamycin 600 mg is permitted as an alternative to amoxycillin/clavulanic acid for patients with hypersensitivity to penicillin. Ciprofloxacin is omitted for participants with hypersensitivity.
 
Arm C: Continue Ig. Participants will continue treatment with their current Ig replacement schedule. Participants will receive monthly (every 4 weeks \pm 1 week) intravenous immunoglobulin at a dose of 0.4g/kg, modified to achieve an IgG trough level of at least lower limit of age-specific serum IgG reference range. For patients who have already had their Ig dose titrated to IgG trough level, they may continue on their current monthly dose of Ig replacement. SC Ig, weekly, may be used in patients who meet local criteria for home-based self-administration in centres with established SC Ig programs. Dosing is usually given at 100mg/kg/week, modified to achieve an IgG steady state level of at least the lower limit of the serum reference range.
 
Planned treatment duration for all arms (A, B and C) is 12 months.

Trial hypotheses	
 1. Prophylactic oral antibiotics are non-inferior to continuation of Ig replacement for the prevention of severe, and/or recurrent infection in patients with secondary hypogammaglobulinaemia due to B-cell malignancies. 2. A strategy of no antibiotic therapy (with a patient-held emergency antibiotic supply) is non-inferior to the continuation of Ig replacement for the prevention of severe and / or recurrent infection in patients with secondary hypogammaglobulinaemia due to B-cell malignancies.
Primary outcome measure	Primary RATIONAL-PT Endpoint: refer to RATIONAL-PT Core Protocol
Secondary outcome measures	
Secondary RATIONAL-PT Endpoints: refer to the RATIONAL-PT Core Protocol.
 
Secondary Domain-Specific Endpoints:
 
 1. Resumption of Ig treatment over 12 months for patients in Ig cessation treatment arms.

2. PROTOCOL APPENDIX STRUCTURE

The structure of the RATIONAL Platform Trial protocol is different to that used for conventional trials because this trial is adaptive and the description of these adaptations is better understood and specified using a ‘modular’ protocol design.

The protocol has multiple modules, in brief, comprising a Core Protocol (overview and design features of the study); a Statistical Analysis Appendix (details of the current statistical analysis plan and models); Domain-Specific Appendices (DSA) (detailing all interventions currently being studied in each domain); and Region-Specific Appendices (RSA) (detailing regional management and governance).

The Core Protocol contains all information that is generic to the trial, irrespective of the regional location in which the trial is conducted and the domains or interventions that are being tested.

The DSA contains information about the intervention(s), within each domain, because one of the trial adaptations is that domains and interventions will change over time. These Appendices are anticipated to change over time, and each modification to a DSA will be subject to a separate ethics application for approval.

Information that is specific to a particular region in which the trial is conducted is contained within a RSA. This includes information related to local management, governance, and ethical and regulatory aspects. Within each region, only that region’s RSA, and any subsequent modifications, will be submitted for ethical review in that region.

In addition to the Master Statistical Analysis Appendix, a Domain-Specific Statistical Analysis Plan (DSSAP) will be prepared that will outline additional aspects of the statistical analysis for this domain.

4. BACKGROUND AND RATIONALE

4.1. Domain definition

This is a domain within the RATIONAL Platform Trial to test the effectiveness and safety of stopping Ig replacement with or without prophylactic antibiotics compare to continuing Ig replacement.

4.2. Domain-specific background

4.2.1. Overview

4.2.1.1. Duration of Ig replacement – when to cease therapy?

Evidence to guide duration of IgRT and when to cease it is limited. From the most recent Cochrane review,¹ in clinical trials of Ig replacement, the duration of therapy was for a period of between 6 and 12 months, with follow-up not extending beyond 12 months. A recent single-centre, non-randomised study showed that regular Ig replacement was able to be safely stopped in a small cohort of patients with haematological malignancies who received prophylactic antibiotics and an additional emergency-held antibiotic supply to keep at home.² To date, there have been no randomised controlled trials to guide if and when to trial cessation of Ig.

Substantial variation exists in the approach to duration of IgRT and use of alternative therapies, both internationally and within Australia.^{3,4} For patients receiving Ig for this indication, Australian government Criteria state: *“Cessation of Ig therapy should be considered at least after each 12 months” of its use.*⁵ This statement is not evidence-based, and in this group of immunocompromised patients who are highly infection prone and vulnerable, and for whom infection is their highest risk of mortality, such evidence is essential in order to recommend or mandate such a clinical management directive. UK guidelines (2019) advise that it may be appropriate to consider temporary cessation of Ig in the summer,⁶ although at least in Australia from 2009 to 2013, there was no significant seasonal change in IgRT utilisation.⁷ In New Zealand (NZ), Ig approvals are reviewed every 12 months.

There is significant variation in clinical practice with regard to duration of IgRT. In a recent survey of Australian and New Zealand haematologists, 21% reported continuing Ig unless an adverse event occurred, 24% routinely stop after a fixed duration, 15% stop if the patient is in clinical remission with recovery from hypogammaglobulinaemia, 6% stop during summer, and 34% decide on a case-by-case basis.⁴

Our current treatment decisions are not evidence-based because no data exist on optimal duration of IgRT or outcomes after stopping: cessation is recommended, but standard of care regarding the

timing of cessation is not defined. We do not know when or how to predict when it is safe to stop, or what to monitor prior to and after stopping. Therefore, a clinical trial is required to evaluate optimal duration of Ig use and/or outcomes after stopping.

4.2.1.2. Predictors of which patients are at higher risk of infection to guide Ig cessation

The effects of changes in immune function over time and its association with disease status, treatment with chemotherapy, immunotherapy and other targeted agents, IgRT, as well as infection outcomes is not well understood. Monitoring the immune status in patients with haematological malignancies over time receiving various immunomodulatory treatments may provide useful insights into the risks of development of infection. Analysis of potential changes in the immune profiles in these patients and their association with infection outcomes may provide guidance as to which patients may benefit most from Ig or other anti-infective measures such as prophylactic antibiotics, and which patients may safely cease these therapies.

4.2.2. Potential benefits of ceasing Ig therapy

Regular IgRT is associated with hospital day-admissions (for intravenous administration) and known adverse effects associated with Ig use. Common adverse effects include headache, lethargy, nausea/vomiting, allergic reactions, arthralgia, myalgia, hypersensitivity reactions, abdominal pain and dyspnoea. Aseptic meningitis can also occur, although this is less common. Regular use of Ig has also been associated with risk of thromboembolic events.⁸ Renal impairment and renal failure have also been reported in patients receiving IVIg. For patients receiving subcutaneous Ig (SC Ig), there may also be injection site irritation and there is a requirement for training and equipment to self-administer the product. Reduction in use of Ig may help reduce healthcare expenditure on Ig product costs and associated healthcare administration costs.

4.2.3. Potential risks of ceasing Ig therapy

The risks of ceasing Ig therapy are unknown, but the main possible risk of ceasing Ig therapy is the risk of major or recurrent infections. Major or recurrent infections may lead to increased unplanned visits to hospital, admission to hospital and/or intensive care, and treatment with antimicrobial agents and other therapies. Within this protocol, patients who are allocated to cease Ig therapy and who experience a major infection (see below) will be allowed to recommence Ig replacement therapy.

4.2.4. Prophylactic antibiotics as an alternative to continuing Ig therapy

Short-term prophylactic oral antibiotics have been shown to reduce infections by 30-50% in neutropenic haematology patients following chemotherapy,⁹ and in non-haematologic malignancy patients with bronchiectasis,¹⁰ supporting the rationale for their use in acquired hypogammaglobulinaemia. A recent systematic review of prophylactic antibiotics in MM showed infection reduction in the first 3 months after diagnosis, but no mortality difference.¹¹

Some international guidelines recommend a trial of prophylactic antibiotics prior to commencing IgRT.¹² Potential advantages include reduced total healthcare costs, possible improvements to QoL with fewer hospital attendances for infusions, and reduction in Ig adverse effects. On the other hand, antibiotic resistance is a concern with wider use of prophylactic antibiotics.^{10,13} In addition, for patients not receiving IgRT the less frequent clinical interactions due to less frequent attendance at day treatment centres have the potential to result in later diagnosis of any infection, which in turn could lead to poorer outcomes. Therefore, the use of prophylactic antibiotics should be properly evaluated with respect to efficacy, safety, QoL, and healthcare costs.

In addition, our recently completed phase II feasibility trial – the RATIONAL (Role of antibiotic therapy or immunoglobulin on infections in haematology) trial – the first to compare starting Ig vs prophylactic oral antibiotics in 63 patients with newly diagnosed CLL, MM and NHL who, as a result were newly eligible to commence IgRT – demonstrated recruitment feasibility and tolerability of oral antibiotics. Although not powered for clinical outcomes, RATIONAL data suggest no increase in infection outcomes in the antibiotic arm (ACTRN12616001723471).¹⁴

4.2.5. Potential risks of prophylactic antibiotic therapy

Some common adverse events to the prophylactic antibiotics used within this protocol include nausea, vomiting, diarrhoea and rash. Other less common adverse reactions include anaphylaxis and hypersensitivity reactions. Another possible risk of prophylactic antibiotics is development of resistant organisms, but its impact on development of infection is unknown.

4.3. The need for a trial assessing immunoglobulin cessation

IgRT is effective at reducing infection in this setting; however:

- There have been significant changes to patient populations, therapeutic agents and protocols and consequent effects on immune function and supportive care since clinical trials of IVIg were performed.

- IVIg, SC Ig and oral antibiotics all carry risks.
- Effectiveness of Ig compared with other potential options, such as prophylactic antibiotics, in terms of compliance with therapy, clinical outcomes, adverse effects, QoL, and healthcare costs, is unknown.
- Australian national criteria and New Zealand guidelines recommend that a trial of cessation of Ig therapy should be considered at least after each 12 months of treatment, but there are few prospective studies indicating how this could be achieved.
- IVIg and SC Ig costs continue to increase, and haematological malignancies are a growing indication for their use.

No trials powered for clinical outcomes have compared continuing IgRT with Ig cessation with or without prophylactic antibiotics in terms of safety, efficacy and cost-effectiveness. Therefore, a clinical trial is required.

This Domain is designed to assess if Ig therapy for adults with haematological malignancies can be stopped if patients are free of major infection after six months of therapy, and after stopping, whether oral antibiotics should be used to prevent future infection.

4.3.1. Domain hypotheses

- Prophylactic oral antibiotics are non-inferior to continuation of Ig replacement for the prevention of severe, and/or recurrent infection in patients with secondary hypogammaglobulinaemia due to B-cell malignancies.
- A strategy of no antibiotic therapy (with a patient-held emergency antibiotic supply) is non-inferior to the continuation of Ig replacement for the prevention of severe and / or recurrent infection in patients with secondary hypogammaglobulinaemia due to B-cell malignancies.

5. DOMAIN OBJECTIVES

5.1. Aims

The aim of this domain is to determine whether stopping Ig with prophylactic or antibiotics or antibiotics on demand, is as effective as continuing Ig (IVIg or SC Ig) in patients with haematological malignancies and acquired hypogammaglobulinaemia on event-free survival as defined in the Core Protocol.

6. DOMAIN DESIGN

This RATIONAL Platform Trial is an investigator-initiated open-label, randomised controlled adaptive platform trial open in multiple sites. The platform design allows many treatment approaches to be tested simultaneously on different patient subpopulations, within the same framework, and for pre-specified interim analyses that can be used to stop recruitment early to arms showing insufficient evidence of efficacy or overwhelming evidence of efficacy. The platform allows the addition of new domains via protocol amendments and DSAs to answer new questions of interest, including different treatments or patient groups. Details of the overall platform trial design are included in the Core Protocol.

The Stop-Ig domain is randomising participants receiving IgRT to one of 3 study interventions: IgRT cessation with prophylactic antibiotics, IgRT cessation with antibiotics for emergency use and continuation of IgRT.

The Stop-Ig domain was initially opened as a standalone trial, RATIONALISE. The RATIONALISE trial was amended to a platform trial design during the course of the trial, as described in the Protocol History Table. As part of the amendment, the RATIONALISE interventions became the 'STOP-Ig' domain interventions within the larger platform.

7. SELECTION AND WITHDRAWAL OF PARTICIPANTS

7.1. Population

The RATIONAL Platform Trial enrolls patients with acquired hypogammaglobulinemia due to haematological malignancies, including multiple myeloma [MM], chronic lymphocytic leukaemia [CLL] and non-Hodgkin lymphoma [NHL]. This domain is available for patients who are currently receiving IgRT for prevention of bacterial infections due to hypogammaglobulinaemia.

7.2. Eligibility criteria

Patients are eligible for the RATIONAL Platform Trial if they meet all of the platform-level inclusion and none of the platform-level exclusion criteria outlined in the Core Protocol. Patients eligible for the RATIONAL Platform Trial may have conditions that exclude them from this Domain.

7.2.1. Domain inclusion criteria

1. Patients must be receiving Ig (IV or subcutaneous - SC Ig) replacement for prevention of bacterial infections due to hypogammaglobulinaemia for at least 6 consecutive months.
2. Patient is eligible for trial of Ig cessation in the opinion of the treating clinician and local investigator.

3. Willing and able to comply with each of the treatment arms.

7.2.2. Domain exclusion criteria

1. Prior or planned allogeneic haematopoietic stem cell transplantation.
2. Major infection (Grade 3 or higher) in preceding 3 months, and/or current active infection requiring systemic antimicrobial treatment.
3. Already receiving systemic antibiotic prophylaxis for the purpose of preventing bacterial infection (NB: patients may receive antiviral, antifungal and PJP prophylaxis).
4. Intolerance of all trial antibiotic options in either arm A or arm B.
5. Communication, compliance or logistical issues (e.g. living long distance from medical facility) that are likely to limit a patient's ability to take prophylactic or emergency antibiotics, or to obtain urgent medical attention for symptoms of infection.
6. Pregnant or breastfeeding.
7. Severe renal impairment (estimated or measured creatinine clearance of <30mL/min).
8. Previous splenectomy.
9. Previous participation in this domain
10. Treating team deems enrolment in the domain is not in the best interests of the patient.

7.2.3. Intervention exclusion criteria

Nil

7.3. Randomisation

Randomisation will occur following confirmation of participant eligibility for the domain, between the baseline and Stop-Ig Domain Day 1 visit. Randomisation will be conducted through a password-protected secure website using a central randomisation programme. Eligibility for randomisation will be assessed with reference to the Platform-level and Domain-level inclusion and exclusion criteria and there will be no exception to eligibility requirements at the time of randomisation.

8. TREATMENT OF PARTICIPANTS

8.1. Interventions

8.1.1. Interventions

This domain has three interventions:

- Immunoglobulin cessation and commencement of prophylactic antibiotics (Arm A)
- Immunoglobulin cessation without prophylactic antibiotics, with a supply of oral antibiotics immediately available (at home) for emergency use (Arm B)
- Continuation of immunoglobulin replacement at current dose and schedule (Arm C)

8.1.2. Immunoglobulin cessation and commencement of prophylactic antibiotics (Arm A)

Participants will be treated with once daily trimethoprim-sulfamethoxazole (co-trimoxazole) 160mg/800mg, with dose adjustments as listed below, from study day 1. For patients with hypersensitivity to co-trimoxazole, or who are taking a medication with potential for a significant interaction with co-trimoxazole as outlined below, 100mg doxycycline daily will be permitted as an alternative prophylactic antibiotic. If participants encounter cytopenias which are exacerbated by the study antibiotics, participants can be switched to the other antibiotic. Participants must be able to tolerate at least one of the study antibiotics to be eligible for entry into the study.

Medications which cannot be administered with co-trimoxazole include (but are not limited to): antiarrhythmics (dofetilide, amiodarone), antivirals (amantadine/memantine, lamivudine), antineoplastics (paclitaxel), antibiotics (dapsone). Co-trimoxazole may increase the effect of the following agents, and increased monitoring of their drug levels and/or effect is required if co-administered with co-trimoxazole: digoxin, phenytoin, warfarin, oral hypoglycaemics (repaglinide, rosiglitazone, pioglitazone, glipizide), methotrexate, drugs that cause potassium retention (such as ACE inhibitors) and cyclosporin (increased monitoring of renal function).

Medications which cannot be administered with doxycycline include (but are not limited to): isotretinoin, etretinate and methoxyflurane. Doxycycline may increase the effect of the following agents, and increased monitoring of drug levels and/or effect is required if co-administered with doxycycline: warfarin, cyclosporin, phenytoin.

8.1.2.1. *Co-trimoxazole dose adjustments for cytopenias and renal impairment*

For participants with grade 2 or greater anaemia, neutropenia or thrombocytopenia, whether attributed to concomitant medications, underlying haematologic disorder or co-trimoxazole itself, the dose of co-trimoxazole may be reduced by 50% (to 80/400mg daily) at the discretion of the investigator.

Co-trimoxazole dose will be adjusted for participants with renal impairment, defined by eGFR (or, if available, measured creatinine clearance)

eGFR or creatinine clearance	Dose
> 50 mL/Min	Full dose (160/800mg)
30 to 50 mL/Min	50% dose reduction (to 80/400mg)
< 30 mL/Min	Consider switching to doxycycline, or discontinue study treatment

8.1.3. Immunoglobulin cessation without commencement of prophylactic antibiotics (Arm B)

Patients will be provided with amoxycillin/clavulanic acid 1750-2000mg/250mg and ciprofloxacin 750mg to keep at home for initial use if symptoms of infection develop, with immediate review by their treating clinical team, or nearest emergency department or medical practitioner with phone contact to treating team if most practical and as clinically required. Diagnosis and management of the infection will be determined by the severity of the suspected infection and coordinated by the patient's treating team.

For patients with hypersensitivity to penicillin, or taking a medication with a significant interaction with amoxycillin/clavulanic acid, clindamycin 600mg is permitted as an alternative to amoxycillin/clavulanic acid. If the patient has a contraindication to ciprofloxacin, this antibiotic will be omitted from the emergency antibiotics. Contraindications to ciprofloxacin include quinolone hypersensitivity (including nalidixic acid) and concurrent tizanidine.

For participants assigned to Arm B, Day 1 of treatment is considered the date of randomisation.

8.1.4. Continuation of immunoglobulin replacement at current dose and schedule (Arm C)

Participants will continue treatment with their current Ig replacement schedule. The recommended dose of Ig replacement is outline below. For participants assigned to Arm C, Day 1 of treatment is considered the first dose of Ig following randomisation.

8.1.4.1. *Intravenous immunoglobulin (IVIg)*

Participants will receive monthly (every 4 weeks \pm 1 week) intravenous immunoglobulin at a dose of 0.4g/kg, modified to achieve an IgG trough level of at least lower limit of age-specific serum IgG reference range. For patients who have already had their Ig dose titrated to IgG trough level, they may continue on their current monthly dose of Ig replacement.

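### Does the protocol leave the Arm C regimen unsettled by promising the current dose and schedule and also stating an IVIg dose and interval?

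*Protocol*

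**What the plan says.** The Arm C label in section 8.1.1 and the heading of 8.1.4 (repeated in the contents list) read "Continuation of immunoglobulin replacement at current dose and schedule (Arm C". The body of 8.1.4 opens with "Participants will continue treatment with their current Ig replacement schedule" and continues "The recommended dose of Ig replacement is outline below".

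Section 8.1.4.1 then states an IVIg regimen in directive wording: "intravenous immunoglobulin at a dose of 0.4g/kg, modified to achieve an IgG trough level of at least lower limit". The limit meant is that of the reference range, and the interval given is monthly (every 4 weeks ± 1 week). The subsection adds one exception: "For patients who have already had their Ig dose titrated to IgG trough level, they may continue on their current monthly dose".

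The Domain Summary (section 1.1) carries the same Arm C text, including the current-schedule sentence, the IVIg dose and interval, and the exception. It lacks the lead-in that calls the dose recommended. For the subcutaneous route, 8.1.4.2 and the summary describe the dose as what is usually given.

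On prior treatment, section 7.2.1 requires "replacement for prevention of bacterial infections due to hypogammaglobulinaemia for at least 6 consecutive months". Sections 7.2.1 to 7.2.3 set no condition on previous dose, interval or titration.

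**The concern.** Arm C is the reference for both non-inferiority hypotheses in section 4.3.1, and section 10.3 makes treatment open-label. A comparator that sites could deliver in two ways deserves a close look.

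Taken literally, the label tells a site to leave an untitrated IVIg participant's dose alone, while 8.1.4.1 tells it to give the stated dose, adjusted to trough. Continuing the current schedule also cannot be squared with a 3-to-5-week interval for someone treated at a different one. Because 8.1.4 presents the dose as a recommendation and the Domain Summary does not, a site might treat the same text as advice or as instruction depending on which page it opened.

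If many participants were affected, the control regimen could differ between sites after randomisation. It would also be harder to judge adherence in Arm C, and section 8.1.7 lists poor compliance as a reason to discontinue assigned treatment.

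**Working it through.** No power, margin or event figure bears on this point, and this document gives none. The check is a comparison of the passages, with two small pieces of arithmetic.

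**1. Dose wording.** Inputs: the 8.1.1 label, the 8.1.4 heading and lead-in, 8.1.4.1 and the Domain Summary.

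- IVIg, already titrated to trough: the label says current dose, and the exception in 8.1.4.1 allows the current monthly dose. No conflict.
- IVIg, not titrated, current dose equal to the stated trough-adjusted regimen: both texts lead to the same dose. No conflict.
- IVIg, not titrated, current dose different: the label and 8.1.4.1 differ, unless the lead-in makes the dose text advisory. Conflict on a literal reading.
- Subcutaneous: the dose text is descriptive, so it does not clash with the label.

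One of the four cases is affected. The regimen in 8.1.4.1 is itself adjusted to a trough level, so it does not impose one flat dose.

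**2. Interval wording.** Input: every 4 weeks ± 1 week (8.1.4.1 and section 1.1).

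- Shortest interval: 4 − 1 = 3 weeks.
- Longest interval: 4 + 1 = 5 weeks.

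Only an IVIg participant treated outside 3 to 5 weeks meets the current-schedule sentence but not the stated interval. The exception covers dose and not interval, so this applies whether or not the participant has been titrated. The exception refers to a monthly dose, which suggests the text assumes monthly IVIg throughout.

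**3. Do the IV and subcutaneous figures agree?** Inputs: 0.4 g/kg per 4 weeks (8.1.4.1); 100 mg/kg/week and 1:1 conversion (8.1.4.2).

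- 400 mg/kg ÷ 4 weeks = 100 mg/kg/week, which matches the subcutaneous figure.
- Across the interval window: 400 ÷ 5 = 80 and 400 ÷ 3 ≈ 133 mg/kg/week.

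The numbers are consistent with each other. The inconsistency is confined to the wording that introduces them.

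**4. Does the comparison depend on the reading?** The hypotheses in 4.3.1 and the aim in 5.1 set stopping immunoglobulin against continuing it. Neither names a dose or an interval for the comparator. Whether 8.1.4.1 is taken as binding or advisory, Arm C participants are assigned to continue immunoglobulin and Arm A and B participants to stop it, so the randomised contrast is the same. Participants taken off assigned treatment are still followed to month 12 under 8.1.7, so a disagreement about adherence does not by itself end follow-up.

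**The case for a change.** The best case for acting has four parts.

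- The exception for titrated patients would be unnecessary if everyone simply kept their dose, so the text appears to mean that untitrated patients do not. That contradicts the arm's own label.
- The interval conflict cannot be dismissed as a loose heading, because both statements are body text in 8.1.4 and in the Domain Summary.
- Section 2 assigns intervention details to this appendix, so other modules are not the natural place to settle the matter.
- Aligning the wording costs no patients, visits or data.

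Most of this stands as a reading of the text. The passages do not say the same thing, nothing states which governs, and the domain criteria do not keep the affected participants out. Platform criteria are in the Core Protocol, which is not at hand.

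What does not stand is the step from inconsistent wording to a defective comparator. A reconciling reading is available: the lead-in presents what follows as a recommended dose, and 8.1.4.1 is the detail beneath it. The conflict also needs a participant who has had at least six months of immunoglobulin and is on IVIg, and who either remains untitrated at a different dose or is treated outside the 3-to-5-week window. The document gives no sign of how often this occurs. Individualised continued immunoglobulin is a legitimate control, and section 13.1 describes all arms as within normal standard of care.

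**Conclusion.** The wording is inconsistent across the contents list and sections 1.1, 8.1.1, 8.1.4 and 8.1.4.1, but no change to the design or analysis follows. The slip is editorial. These passages should be reconciled when the appendix is next revised, so that they agree on whether the IVIg dose and interval text is binding or advisory. That is a clinical choice for the sponsor, and no view is taken on it here.

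The size of any effect cannot be calculated. The number of affected participants, their current doses and intervals, and the non-inferiority margin are not in this document. No bias is shown in either direction.

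The conclusion rests on two assumptions. The first is that the comparator is continued immunoglobulin as the hypotheses state it, rather than one fixed regimen. The second is that participants in the conflicting cases are few, which is plausible given the trough-adjusted dosing and the monthly pattern the text takes for granted, but which this document cannot confirm.

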10. ASSESSMENTS AND FOLLOW-UP

10.1. Domain Schedule of Assessments

All participants enrolled in the platform and any one of the domains are to be followed according to the Schedule of Assessments in the core platform protocol. The following additional assessments are to be completed for all participants enrolled in this domain. All visits for the domain must align with the core protocol visits and visit windows, for example the Month 1 visit on the domain is the Month 1 visit on the platform schedule of assessments.

Period	Screening	Treatment Period													Follow-up
		Visit BL	Visit D1*	Visit M1	Visit M2	Visit M3	Visit M4	Visit M5	Visit M6	Visit M7	Visit M8	Visit M9	Visit M10	Visit M11	Visit M12/EOT
Procedure															
Domain Informed Consent	X														
Treatment details [#]	X														
Domain eligibility assessment	X														

*D1 is Day 1 of trial treatment for participants on Arm A and Arm C. D1 is day of randomisation for participants on Arm B. BL and D1 assessment may occur on the same day. D1 must occur no more than 7 days after randomisation.

[#]Updated information on treatment for underlying malignancy if this has changed from platform enrolment

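### Do the arm-specific Day 1 definitions and the 7-day limit on Day 1 conflict with four-weekly IVIg in Arm C?

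*Protocol*

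**What the plan says.** Day 1 depends on the arm.

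- **Arm A** (Protocol 8.1.2): the prophylactic antibiotic is taken "from study day 1".
- **Arm B** (8.1.3): "Day 1 of treatment is considered the date of randomisation".
- **Arm C** (8.1.4): "Day 1 of treatment is considered the first dose of Ig following randomisation". The patient stays on the current Ig schedule. IVIg is given every 4 weeks, plus or minus 1 week (8.1.4.1), and subcutaneous Ig weekly (8.1.4.2).

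The footnote to the schedule in 10.1 repeats the split: "D1 is Day 1 of trial treatment for participants on Arm A and Arm C", and the day of randomisation for Arm B. It adds "BL and D1 assessment may occur on the same day" and "D1 must occur no more than 7 days after randomisation". Section 7.3 places randomisation "between the baseline and Stop-Ig Domain Day 1 visit" and mentions neither the limit nor the infusion date. Section 8.1.6 counts the 12 months from Day 1. On visits, 10.1 states: "All visits for the domain must align with the core protocol visits and visit windows".

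**The concern.** Two things look wrong.

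First, the clock for the visits and for the 12-month treatment period starts at randomisation in one arm and at first treatment in the other two. Allocation is open label (10.3), so the start of follow-up depends on a known allocation.

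Second, a 7-day limit sits badly with a 28-day infusion cycle. A site that randomises in mid-cycle learns only afterwards that the patient is in Arm C. It must then either breach the limit or move the infusion off the patient's schedule. Arm B meets the limit automatically and Arm A can start on any day within it, so such deviations would fall only on the control arm. The allowance for baseline and Day 1 on the same day seems to add a trap: a patient randomised just after that day's infusion has no further dose for about three to four weeks.

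**Working it through.** The protocol gives no figure on this point, so there is none to reproduce. The check has four steps.

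**1. Do the sections contradict each other?** Sections 8.1.2 to 8.1.4 and the 10.1 footnote define Day 1 in the same way for each arm. Three rules bear on Arm C:

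- randomisation precedes the Day 1 visit (7.3);
- Day 1 is the next Ig dose after randomisation (8.1.4);
- Day 1 falls within 7 days of randomisation (10.1).

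All three hold together when randomisation takes place shortly before an infusion. Allocation is unknown beforehand, so a site can comply only by timing every IVIg candidate this way. The rule is therefore already in the plan, although 7.3 does not repeat it.

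**2. What happens if sites do not time randomisation?** Let u be the days since the last infusion at randomisation.

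Inputs: a 28-day interval with an earliest in-window dose on day 21 (8.1.4.1), and a limit of 7 days (10.1).

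Assumptions: u is uniform over the cycle, and the one-week window also applies to the interval from the last infusion before randomisation. The protocol states neither.

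| Randomised at | Next dose within 7 days? | Share |
|---|---|---|
| u ≥ 21 | yes, on schedule | 7/28 = 25% |
| 14 ≤ u < 21 | only if brought forward within the window | 7/28 = 25% |
| u < 14 | no, since u + 7 < 21 | 14/28 = 50% |

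The on-schedule share is 7/21 = 33% at a 21-day interval and 7/35 = 20% at 35 days. Weekly subcutaneous Ig always fits (7/7). If a share s of Arm C uses it, the ceiling over all of Arm C is 0.50 × (1 − s): 50%, 40% and 25% for assumed s of 0, 0.2 and 0.5. With timed randomisation it is about 0%.

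*Same-day case.* If randomisation comes before that day's infusion, Day 1 is that day and the offset is 0. If it comes just after, the next dose is 21 to 28 days away, which is 21 − 7 = 14 to 28 − 7 = 21 days past the limit. But 8.1.4 counts only a dose given after randomisation, so the earlier infusion cannot serve as Day 1. The plan does not permit this order; it makes it a plain breach of the limit.

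**3. How far apart are the clocks?** With the limit kept, Arm B has offset 0 and Arms A and C have 0 to 7 days. The largest difference is 7/365 = 1.9% of 12 months. Section 8.1.6 also lets patients stay on their treatment after 12 months.

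**4. Would a change gain anything?** Two changes suggest themselves.

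- *A sentence in 7.3 that IVIg candidates are randomised when the next dose is due within 7 days.* The wait would be max(0, 21 − u): 21/28 = 75% wait, on average 21/2 = 10.5 days among them, (21²/2)/28 = 7.9 days over all, and 21 at most. A site that follows the footnote and keeps infusions on schedule has this wait already. Nor does the sentence secure compliance: a dose due on day 7 and given a week late, within the window, puts Day 1 at 7 + 7 = 14 days. The limit in 10.1 still does the work.
- *One clock from randomisation in all arms.* This removes an offset of at most 7 days, but it cuts Arm A's treatment within the 12 months by up to 7 days. It would also move Day 1 visits that must match a Core Protocol schedule not available here.

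**The case for a change.** The best case for a change is practical. Staff who randomise read 7.3, not a footnote to the schedule combined with an arm-specific dosing section. The difficulty appears only once allocation is known, when randomisation cannot be undone, and only the control arm is exposed. One sentence, applied before allocation, would need no extra patients or visits and would change no dose or schedule.

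Part of this stands. Section 7.3 is silent, the exposure is one-sided, and a pointer there to the limit in 10.1 would be a harmless convenience. But it would repeat a rule that already binds. Nothing in the document suggests that sites overlook the footnote, and the 50% figure arises only if they do. The difference in clock origin is also an ordinary choice: Arm B has no scheduled drug or infusion to mark a start, so the date of randomisation serves.

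**Conclusion.** No change to the plan is needed. The definitions of Day 1 are consistent, and taken together the rules already require randomisation shortly before the next infusion for patients on IVIg. A site that follows them obtains an offset between arms of at most 7 days (1.9% of 12 months). What remains is a detail that 7.3 leaves to 10.1, and sites can fill it sensibly.

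The 50% is an upper bound for IVIg patients in Arm C. It rests on a 28-day interval, randomisation wholly untimed, and the one-week window applied to the dose before randomisation. With timed randomisation it is about 0%, and patients on weekly subcutaneous Ig are not affected.

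No bias in event-free survival can be claimed. Its time origin is set in the Core Protocol; if that origin is randomisation, the Day 1 difference touches only visit dates and the end of the 12-month treatment period.
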